2.3 Secondary endpoints

The secondary endpoints are:

- The change in CO at the pacing frequency corresponding to the greatest reduction in PCWP compared to the intrinsic heart rate
- The change in SV at the pacing frequency corresponding to the greatest reduction in PCWP compared to the intrinsic heart rate
- The change in peripheral oxygen extraction at the pacing frequency corresponding to the greatest reduction in PCWP compared to the intrinsic heart rate
- The change in SWV for each pacing frequency. The SWV at the intrinsic heart rate is defined as the average of the SWV at the intrinsic heart rate heart rate before and after each pacing step.

Cardiac output is measured via the direct Fick principle, dividing VO_2 by the peripheral oxygen extraction (SaO_2 - SvO_2). SV is calculated as CO divided by HR.

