5.4.3 Pharmacovigilance / Materiovigilance

Any incidents related to the use of a medical device should be reported to the Competent Authorities according to the materiovigilance guidelines.

6 Statistics and data analysis

A study-specific Statistical Analysis Plan (SAP) will be developed by the Sponsor, to supplement the information below with further details.

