6.1 Sample size determination

The sample size calculation is based on the expected difference in PCWP between pacing conditions. A power analysis determined that 16 participants are required to achieve a power of 80% and a significance level of 5% (two-sided), assuming a mean difference of -2 mmHg and a standard deviation of 2.5 mmHg. To account for potential dropout, the study will enroll 20 participants.

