6.2 Statistical analysis

This is a prospective, single-arm, multicentre, interventional study in which each patient serves as their own control:

- A two-sided significance level of 0.05 will be used for all statistical tests.
- Data will be analyzed using Python, SPSS and Stata statistical software.
- Descriptive statistics of baseline variables will be used to summarize baseline characteristics.
 - Categorical variables will be presented as number and percentage.
 - Continuous variables will be presented as mean \pm standard deviation or median with interquartile range, depending on the Shapiro-Wilk test for normality.
- Comparison of hemodynamic parameters (PCWP, CO, SV, peripheral oxygen extraction) and SVV will be performed using paired student t-test or Wilcoxon-Mann Whitney test whichever will be appropriate.
- Pearson's or Spearman's correlation coefficients, whichever will be appropriate, will be computed to assess the relationship between changes in PCWP and changes in SVV

Endpoint	Statistical analysis methods
Primary	paired student t-test or Wilcoxon-Mann Whitney test
Secondary	paired student t-test or Wilcoxon-Mann Whitney test
Exploratory	descriptive statistics, Pearson's or Spearman's correlation coefficient

7 Data handling

A study-specific Data Management Plan (DMP) will be developed by the Sponsor providing a.o. further details on data flows, data handling, processing and discrepancy management.

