 - Set the pacemaker to DDD mode with a lower rate of **20** bpm above the intrinsic heart rate, rounded to the nearest decimal
 - Adjust AV-delay to the optimal setting and measure shear wave velocity
 - 10 seconds after AV delay optimization: PCWP measurement
- Pacing-off:
 - Reprogram the pacemaker to back-up mode
 - Measurement of SWV
 - 10 seconds after pacemaker reprogramming: PCWP measurement
- Pacing-on
 - Set the pacemaker to DDD mode with a lower rate of **40** bpm above the intrinsic heart rate, rounded to the nearest decimal
 - Adjust AV-delay to the optimal setting and measure shear wave velocity
 - 10 seconds after AV delay optimization: PCWP measurement
- Pacing-off:
 - Reprogram the pacemaker to back-up mode
 - 10 seconds after pacemaker reprogramming: PCWP measurement
- Pacing-on:
 - Set the pacemaker to DDD mode with a lower rate of **60** bpm above the intrinsic heart rate, rounded to the nearest whole number
 - Adjust AV-delay to the optimal setting and measure shear wave velocity
 - 10 seconds after AV delay optimization: PCWP measurement
- Pacing-off:
 - Reprogram the pacemaker to back-up mode
 - Measurement of SWV
 - 10 seconds after pacemaker reprogramming: PCWP measurement
 - After 4 respiratory cycles: collection of arterial and mixed venous blood samples
- Pacing-on
 - Set the pacemaker to DDD mode with a lower rate corresponding to previously determined rate with the greatest reduction in PCWP
 - 10 seconds after pacemaker reprogramming: PCWP measurement
 - After 4 respiratory cycles: collection of arterial and mixed venous blood samples
- Pacing-off: reprogram to pacemaker back-up mode

HR, VO₂, RER and will continuously be measured.

Each pacing-off (DDD 40 back-up pacing mode) and pacing-on (temporary DDD pacing via programmer) period will take 40 seconds.

The optimal AV-delay will be determined via iterative evaluation of the mitral valve inflow by transthoracic echocardiography. This will be followed by SWV measurements, performed over a 12-second period.

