PCWP will be measured as the average end-expiratory value over four consecutive respiratory cycles, following a 10-second period to allow for hemodynamic stabilization. By comparing each PCWP value to the average of the PCWP measured during the pacing-off periods immediately before and after the pacing-on phase, we aim to minimize the impact of spontaneous hemodynamic variability and carry-over effects (41). The heart rate associated with the greatest reduction in PCWP will be repeated as the final pacing-on step, during which CO will be measured by collecting arterial and mixed venous blood samples (direct Fick principle). If two pacing rates result in an equal reduction in PCWP, the lower pacing rate will be selected. If no reduction in PCWP is observed with accelerated pacing, the heart rate corresponding to the smallest increase in PCWP will be selected for the final pacing-on period instead. In this final step, PCWP will be measured again to verify that it remains consistent with the initial PCWP at the same pacing rate. Only the initial PCWP measurement at the optimal pacing rate will be used in our analyses assessing changes in PCWP compared to the intrinsic heart rate.

The pacing rate will never exceed the APMHR, calculated based on Takana's equation (42). If this threshold would be reached, the protocol will be stopped at the pacing step prior to exceeding the APMHR, only followed by the final pacing step in which the pacing rate associated with the greatest reduction in PCWP is repeated.

16 APPENDIX 4: Detailed description of the study protocol during exercise

The following section provides a stepwise description of the pacing protocol performed during exercise (Figure 4):

- Pacing-off:
 - Measurement of SWV
 - PCWP measurement after 10s of cycling
- Pacing-on:
 - Set the pacemaker to DDD mode with a lower rate of **10** bpm above the intrinsic heart rate, rounded to the closest decimal and with dynamic AV-delay settings
 - Evaluate mitral inflow pattern on echocardiography for evidence of E-wave truncation; if truncation is observed, the AV-delay will be adapted accordingly.
 - Non-invasive measurement of BP
 - Measurement of SWV
 - 10s after the last change in pacemaker settings: PCWP measurement
- Pacing-off:
 - Reprogram the pacemaker to back-up mode
 - Measurement of SWV
 - 10 seconds after pacemaker reprogramming: PCWP measurement
- Pacing-on:

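### Appendix 3 lists no resting shear wave velocity reading between the +40 and +60 bpm steps, although section 2.3 needs it for the baseline at both rates

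*Combined protocol and SAP*

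**What the plan says.** Section 2.3 lists the change in SWV for each pacing frequency among the secondary endpoints and fixes the comparator: the intrinsic-rate value is "defined as the average of the SWV at the intrinsic heart rate heart rate before and after each pacing step". The synopsis also describes SWV at each pacing frequency relative to the intrinsic rate.

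Section 4.2.2 refers to Appendix 3 for the detailed resting procedure and to Appendix 4 for exercise. In Appendix 3 the resting pacing-off between +40 and +60 bpm has two entries: the return to back-up pacing, and "10 seconds after pacemaker reprogramming: PCWP measurement". No SWV entry appears there.

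Two general statements in Appendix 3 also bear on the point. After the description of AV-delay optimisation it says "This will be followed by SWV measurements, performed over a 12-second period". On period length it says "Each pacing-off (DDD 40 back-up pacing mode) and pacing-on (temporary DDD pacing via programmer) period will take 40 seconds".

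Section 6.2 plans a correlation to "assess the relationship between changes in PCWP and changes in SVV" (from the context, SVV there means SWV). Section 6 leaves further detail to a later document: "A study-specific Statistical Analysis Plan (SAP) will be developed by the Sponsor, to supplement the information below with further details".

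**The concern.** The endpoint definition and the step list do not match. A before-and-after baseline needs an SWV reading in every pacing-off that adjoins a pacing step. The period between +40 and +60 adjoins two steps: it supplies the reading after +40 and the reading before +60. One missing line therefore removes half of the defined baseline at two rates.

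Each participant has a single invasive study visit, so a reading not taken then cannot be recovered. Both sites work from the same list, and nothing in section 6.2 says what to do when a before or after reading is absent. Each site or analyst could then choose a different substitute after the data are in. For PCWP, Appendix 3 explains why the adjacent periods are averaged: "we aim to minimize the impact of spontaneous hemodynamic variability and carry-over effects". Section 2.3 adopts the same form of baseline for SWV, and at these two rates the list does not deliver it.

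**Working it through.** The plan gives no computed figure for SWV. Its only calculation, the sample size in section 6.1, concerns PCWP and does not enter here. The check is a reading of the lists against the definition.

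**Formula from section 2.3.** SWV change at rate r = SWV(on, r) − [SWV(off before r) + SWV(off after r)] / 2. All three readings are needed.

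**Measured pacing-off periods at rest (Appendix 3).**

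| Pacing-off | SWV listed | PCWP listed |
|---|---|---|
| before +20 | yes | yes |
| between +20 and +40 | yes | yes |
| between +40 and +60 | no | yes |
| after +60 | yes | yes |

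The pacing-off that ends the sequence carries no measurements and is not counted. In Appendix 4 the four measured exercise pacing-offs (before +10, between +10 and +30, between +30 and +50, after +50) all list SWV and PCWP, and the sequence is repeated at 25 W.

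**Resting SWV changes.** SWV is listed in all three pacing-on steps.

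| Rate | Before | After | Derivable as defined |
|---|---|---|---|
| +20 | yes | yes | yes |
| +40 | yes | no | no |
| +60 | no | yes | no |

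**Does other text supply the reading?**
- The 12-second sentence follows AV-delay optimisation, so it describes pacing-on.
- The averaging rule in the Appendix 3 narrative is stated for PCWP.
- The data list in section 7.1.1 names SWV during the study protocol but gives no timing.
- The visible caption of Figure 3 does not mention SWV, and the figure itself is not available.

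**Size.**
- Per patient completing +60: 3 − 1 = 2 of 3 resting changes.
- With all 20 enrolled completing +60: 20 × 2 = 40 of 20 × 3 = 60.
- With the 16 that section 6.1 requires: 16 × 2 = 32 of 16 × 3 = 48.
- Over rest, 10 W and 25 W: 2 of 3 × 3 = 9 rate-by-condition changes, or 22%.

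These are upper bounds. Appendix 3 stops the sequence before the age-predicted maximal heart rate is exceeded. A patient stopped before +60 has no +60 change to lose. A patient stopped at +20 loses nothing through this omission. The documents do not allow the number of such patients to be estimated.

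**After the fix.** With an SWV reading in the pacing-off between +40 and +60, 3 of 3 resting changes are derivable. The sample size does not change.

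**The case against.** The strongest reply is that the protocol already requires the reading. Section 2.3 has the same standing as Appendix 3, and staff who apply both would record SWV in every adjoining pacing-off. Section 2.4 says patients undergo the protocol of Figures 3 and 4, Appendix 3 presents its list as a description of Figure 3, and that figure may show the reading. Every other measured pacing-off lists SWV, so this looks like a lost line and not a choice. The stakes are also small. SWV is a secondary endpoint, section 6.1 sizes the trial on PCWP only, the +20 change at rest and all exercise changes are intact, and the correlation in section 6.2 is exploratory and names no rate or condition.

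Most of this stands. It limits the finding to an inconsistency in the text. It does not remove it: the step list is the detailed instruction for the visit, and as written it leaves out a reading that the endpoint definition needs.

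A reader might go further and infer that the resting SWV data at +40 and +60 will be lost, or that nothing can be estimated there. The documents do not support that. The reading may be taken in practice, and even without it a one-sided comparison would remain (before only at +40, after only at +60). That would differ between the two rates and would not be the section 2.3 definition. Nor can 40 of 60 be read as an expected loss, because the heart-rate cap may stop some patients earlier.

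**Conclusion.** The inconsistency is real and wrong as written, and it is confined to one secondary endpoint at rest. Under the Appendix 3 list, only the +20 change meets the section 2.3 definition. Up to 2 of 3 resting SWV changes per patient, at most 40 of 60 with 20 enrolled, do not. The exploratory PCWP-SWV correlation inherits the gap wherever it uses those two resting rates.

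The conclusion assumes that sites follow the written list and that Figure 3 does not show the reading. If the figure does show it, list and figure disagree and still need to be aligned. The primary endpoint is not affected, because PCWP is listed in every measured pacing-off. The exercise SWV endpoint is not affected either.

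**What to change.** In Appendix 3, add an SWV measurement to the resting pacing-off between +40 and +60 bpm, worded and placed as in the pacing-off between +20 and +40. Check Figure 3 and make it agree with the list.

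The cost is one protocol line. Appendix 3 gives 12 seconds for the recording during pacing-on. Assuming the same length in pacing-off, it falls within a 40-second period that already holds the reading in the other three measured resting pacing-offs. Recording time is 12 s × 20 = 240 s, or 4 minutes over 20 patients. The sample size and the analysis methods stay as they are. The line should be in place before visits are run, because a missed reading cannot be added later.

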2.4 Study design

This is a **prospective interventional** study, as it actively adjusts pacing rate and AV delay in real time to assess their acute effects on PCWP at rest and during exercise.

The study is a **single arm** study. All patients undergo the pacing protocol (Figure 3 and 4) as an internal pairwise comparison is made between different pacing conditions and the intrinsic heart rate.

The study is **unblinded**. All measurements will be performed bedside, allowing patients to follow the different steps of the protocol. As a result, they will naturally become aware of pacing adjustments, making partial blinding unfeasible. While this may introduce some expectation bias in subjective measures such as palpitations or exertion intolerance, the primary (PCWP) and secondary endpoints (CO, SV, peripheral oxygen extraction, SWV) are objective physiological measures. Therefore, the absence of blinding does not compromise the validity of the results.

The study is **multicenter**, as both UZ Leuven and Jessa Hospital will recruit patients and implement the study protocol.

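### Section 2.4 rules out any effect of open measurement on validity by considering participant expectation only; a reading tilt tied to the pacing state would inflate the PCWP estimate and its false-positive rate

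*Combined protocol and SAP*

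**What the plan says.** Section 2.4 (Study design) calls the study unblinded. Its reasoning is that patients will notice pacing changes, that this could colour subjective measures such as palpitations, and that PCWP, cardiac output (CO), stroke volume (SV), oxygen extraction and SWV are objective. It ends: "Therefore, the absence of blinding does not compromise the validity of the results".

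The reading rule is in Appendix 3: "PCWP will be measured as the average end-expiratory value over four consecutive respiratory cycles", after a 10-second stabilisation period. Each pacing-on value is compared with the mean of the pacing-off values just before and after it. The rate with the greatest PCWP reduction is repeated as the last pacing-on step, when the blood samples are drawn. PCWP is measured again there as a consistency check, but the initial reading is the one analysed. Appendix 4 carries these rules over to exercise.

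Section 2.2 defines the primary endpoints as the PCWP change at each pacing rate. Section 2.3 defines CO, SV and oxygen extraction at the rate with the greatest reduction. Section 6.2 states: "A two-sided significance level of 0.05 will be used for all statistical tests". Section 6 promises a supplementary SAP.

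**The concern.** The premise of section 2.4 concerns participants, while its conclusion covers the whole study. Reader knowledge is a separate route to bias and is not discussed. In Appendices 3 and 4, pacemaker programming, AV-delay adjustment, SWV and PCWP follow one another within each step, and the final rate depends on PCWP values obtained minutes earlier. Those values are therefore read live by a team that knows the pacing state. Section 2.1 gives that team a directional hypothesis: pacing lowers PCWP.

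The rule leaves some choices open: which four breaths, how end-expiration is identified, and which beats are rejected. No section provides for a scripted, masked or second derivation. Section 7.1.1.1 lists raw time series for the CPET data but lists PCWP only as a parameter, so a stored pressure trace is not assured. Section 7.3 dispenses with independent monitoring.

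Every primary contrast sets on-readings against off-readings in the same patient. A consistent difference in how the two are read does not average out over patients, and bracketing does not remove it, because both bracketing values carry the off label.

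**Working it through.** **Inputs from the protocol.** Section 6.1: 16 evaluable participants for 80% power at a two-sided 5% level, "assuming a mean difference of -2 mmHg and a standard deviation of 2.5 mmHg"; and "To account for potential dropout, the study will enroll 20 participants". Section 6.2: primary test "paired student t-test or Wilcoxon-Mann Whitney test". Section 2.2: three rates at rest and three at each of two workloads, so 3 + 3 × 2 = 9 primary contrasts.

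**Input not in the protocol.** The reading tilt b, meaning the systematic part of the on-minus-off difference that comes from reading alone. It is assumed, over 0.25 to 2 mmHg.

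**Step 1: reproduce the sample size.** Take 2.5 mmHg as the SD of the paired difference. An exact paired t-test has power 79.0% at n = 14, 82.1% at n = 15 and 84.8% at n = 16, so 15 are needed. Allowing for a signed-rank test with efficiency 3/π gives 15 × π/3 = 15.7, so 16. With 20% dropout, 16/0.8 = 20. If 2.5 mmHg were instead a per-group SD in a two-sample comparison, 25 per group would be needed. The plan's figure therefore fits the paired-difference reading, although section 6.1 does not say so.

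**Step 2: difference needed for p < 0.05.** This is t(0.975, n−1) × 2.5/√n.
- n = 16: 2.131 × 0.625 = 1.33 mmHg
- n = 20: 2.093 × 0.559 = 1.17 mmHg

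These are 67% and 58% of the planned 2 mmHg.

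**Step 3: false-positive rate under a tilt, true effect zero.** The t statistic is noncentral with λ = b√n/2.5. The two-sided rejection probability is 1 − F(t; n−1, λ) + F(−t; n−1, λ), where t is the critical value. For b = 0.5, λ = 0.5/0.625 = 0.80 (n = 16) and 0.5/0.559 = 0.89 (n = 20).

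| Assumed tilt (mmHg) | Share of 2 mmHg | n = 16 | n = 20 |
|---|---|---|---|
| 0 | 0% | 5.0% | 5.0% |
| 0.25 | 12.5% | 6.6% | 7.1% |
| 0.5 | 25% | 11.6% | 13.6% |
| 1.0 | 50% | 32.2% | 39.7% |
| 1.5 | 75% | 61.2% | 72.1% |
| 2.0 | 100% | 84.8% | 92.4% |

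**Step 4: nine contrasts together.** Simulation (10,000 trials per setting, n = 16 and 20, assumed correlation 0, 0.5 or 0.8 between the nine differences) gives the chance of at least one significant false reduction: 9-21% with no tilt, 29-72% at 0.5 mmHg and 60-99% at 1.0 mmHg. The no-tilt figure is the separate cost of testing nine contrasts without adjustment. The rise above it is due to the tilt.

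**The case against.** The protocol already constrains the reading. The wait, the end-expiratory convention, the four consecutive breaths and the bracketing off-values apply to on and off periods alike, and a repeat PCWP is taken at the chosen rate. A script could go in the promised SAP. Nothing in the documents shows that a tilt exists, or how large it would be. All of this stands. The existing rules make a large tilt less likely, but they do not exclude one tied to the label, and section 2.4 as worded says no further protection is needed.

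Three stronger readings are tempting but unsupported.

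- **That a small tilt would manufacture the effect sought.** A 0.5 mmHg tilt shifts the estimate by 0.5 mmHg. An observed difference of 1.17-1.33 mmHg is needed for significance, and a tilt of 2 mmHg would be needed to produce the whole planned effect.
- **That choosing the best rate from known-state readings biases the primary result.** Section 2.2 defines the primary contrasts at each rate, so the choice leaves them unchanged. A tilt equal at all rates does not alter which rate is chosen either. CO, SV and oxygen extraction come from VO2, heart rate and blood saturations, so a tilt reaches them only through the chosen rate, and only if it differs between rates. Exaggeration from taking the best of three is a selection matter that masked reading would not cure.
- **That SWV is read unmasked.** Appendix 3 has SWV acquired straight after AV-delay adjustment, over 12 seconds. It does not say who derives the values or when. The gap is that nothing is specified.

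**Conclusion.** The concern holds in limited form. The conclusion in section 2.4 does not follow from its argument, and the protocol specifies no derivation of PCWP or SWV that is independent of the pacing label. For PCWP, live reading with the state known is a firm inference from the same-visit choice of rate.

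With no true effect, the per-contrast two-sided error rate would rise from 5% to about 12-14% at a 0.5 mmHg tilt and to about 32-40% at 1.0 mmHg, with the estimate shifted by the same 0.5 or 1.0 mmHg. These figures rest on an assumed tilt, on 2.5 mmHg being the SD of the paired difference, and on the paired t-test. They show how sensitive the design is and do not predict that such a tilt will occur. The sample size is not in question. The change should be made, and before enrolment, because a pressure trace that was not stored cannot be recovered.

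**What to change.** 1. In section 2.4, limit the sentence on validity to participant expectation, and state how reader knowledge is handled.
2. Require the pressure trace to be stored, with a time mark at each pacemaker setting change. Also name the start mark for the opening off period of each series, where no reprogramming step is listed.
3. Use the live PCWP only to choose the final step. Derive the analysed PCWP from the stored trace with one script, fixed in advance and identical for on and off periods: the first four complete breaths from 10 seconds after the last setting change, with fixed rules for end-expiration and beat rejection.
4. Define the CO, SV and oxygen-extraction endpoints at the rate actually repeated in the final step, since the blood is sampled there. Report how often the scripted best rate differs from it.
5. Have the study team read SWV from coded clips, in random order and without step labels.

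Cost: trace export, a short script (section 6.2 already plans for Python) and some analysis time. Sample size, visit and participant burden are unchanged. Two limits remain: the documents do not confirm that the trace can be exported, so both sites must check, and heart rate cannot be fully hidden on SWV clips.
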